3.1.3. Group B Phase 1b (Dose Escalation): Entospletinib + decitabine

Note: At the time of this amendment, Group B Phase 1b had completed enrollment.

During the dose escalation, the initial dosing level for the 1st cohort is defined as level 0 in table below. Intra-subject dose escalation will not be allowed.

Table 3-2. Group B Entospletinib Dose Escalation Table

Dose Level	Entospletinib	Decitabine
0	200 mg	20 mg/m ²
1	400 mg	

Entospletinib lead-in (Cycle 0): ENTO will be administered orally every 12 hours on Days 1-14 as a single agent during the lead-in (Cycle 0). However, decitabine treatment may be started earlier, after 5 days of exposure to ENTO, if the Principal Investigator agrees with the treating physician that treatment should start sooner. Examples of such situations may include but are not limited to:

- White blood cell count is increasing and greater than 20,000/ μ L
- Leukemic related complications that in the opinion of the treating physician require the initiation of cytotoxic chemotherapy sooner

Hydroxyurea is allowed during the lead-in period per investigator discretion and after discussion with the medical monitor. Hydroxyurea should be discontinued prior to initiating decitabine induction.

A bone marrow aspirate for disease assessment will be performed at the end of the monotherapy lead-in period (ie, Cycle 0 Day 14 or after the minimum 5 days of ENTO), and prior to initiating decitabine induction.

Entospletinib + decitabine induction (Cycles 1-4): ENTO will be administered orally every 12 hours on Days 1-28 in combination with decitabine on Days 1-10 of every 28-day cycle for at least 2 but no more than 4 cycles of induction chemotherapy.

A bone marrow aspirate and biopsy sample will be collected for disease assessment and biomarker research at the end of every 2 cycles (Cycle 2 Day 28 and Cycle 4 Day 28) or as clinically indicated. Subjects with cytogenetic and molecular mutations at screening must have cytogenetic and molecular mutation testing repeated at subsequent bone marrow examinations (Cycle 0 Day 14, Cycle 1 Day 28, count recovery, End of Study).

If the subject achieves < 5% blasts by morphology and flow cytometry or has evidence of clinical benefit after completing 2-4 induction cycles but is not eligible for SCT, the subject will have the option to receive maintenance therapy with ENTO in combination with decitabine. Subjects with persistent evidence of disease (ie, blasts \geq 5%) after Cycle 2 may receive up to 2 more induction cycles until subject achieves < 5% blasts.

If < 5% blasts by morphology and flow cytometry is not achieved or the subject does not show evidence of clinical benefit after 4 induction cycles, the subject is considered a treatment failure and will have met study efficacy endpoint criteria, but will remain on study for required study-related follow-up procedures.

Entospletinib + decitabine maintenance (at least 2 cycles): ENTO will be administered orally every 12 hours on Days 1-28 in combination with decitabine on Days 1-5 of every 28-day cycle. A bone marrow aspirate sample will be collected at the end of every 4 cycles (eg, Cycle 4 Day 28, Cycle 8 Day 28) or as clinically indicated for disease assessment and biomarker research. Subjects who achieve CR/CRi that is stable for 2 consecutive bone marrow evaluations are not required to have further bone marrow aspirate samples collected, unless clinically indicated. After completing at least 2 cycles, the subject may proceed to SCT. If not eligible for SCT, subjects will have the option to continue on maintenance therapy with ENTO in combination with decitabine. Subjects who are intolerant of decitabine may switch to ENTO monotherapy maintenance at any time after completing the first 2 cycles. Maintenance may continue as long as the subject is experiencing benefit and does not meet the criteria for study treatment discontinuation.

Entospletinib maintenance (up to 12 cycles): ENTO will be administered orally every 12 hours as monotherapy on Days 1-28 of each 28-day cycle and continued for up to 12 cycles as long as the subject is experiencing benefit and does not meet the criteria for study treatment discontinuation. A bone marrow aspirate sample will be collected for disease assessment and biomarker research at the end of every 4 cycles (eg, Cycle 4 Day 28, Cycle 8 Day 28) or as clinically indicated. Subjects who achieve CR/CRi that is stable for 2 consecutive bone marrow evaluations are not required to have further bone marrow aspirate samples collected, unless clinically indicated. Extension of maintenance may occur on an individual basis if approved by the Principal Investigator.

If a subject discontinues study treatment (eg, as a result of an AE), every attempt should be made to keep the subject in the study to perform the required study-related follow-up and procedures. If this is not possible or acceptable to the subject or investigator, the subject may be withdrawn from the study.

Note: At the time of this amendment, Group B Phase 1b had completed enrollment.

3.1.4. Group B Phase 2 (Dose Expansion): Entospletinib + Hypomethylating agent

The overall safety of ENTO in combination with a hypomethylating agent (decitabine or azacitidine) will be evaluated. As part of the safety run-in, ENTO 400 mg in combination with azacitidine 75mg/m² will be administered to 6 evaluable subjects.

Following completion of the safety run-in (DLT window, Section 3.2), the safety of the azacitidine arm will be reviewed to determine if enrollment of the expansion cohort may proceed with azacitidine. If 2 or more subjects experience DLT, all ongoing subjects in the safety run-in will be discontinued and the azacitidine arm will be dropped from the study. If Phase 2 proceeds with an azacitidine arm, subjects will be randomized to receive ENTO in combination with either decitabine or azacitidine.

Note: At the time of this amendment, Group B Phase 2 safety run-in had completed enrollment.

Entospletinib Safety lead-in (Cycle 0): ENTO 400 mg will be administered orally every 12 hours on Days 1-14 as a single agent during the lead-in (Cycle 0). However, chemotherapy with the assigned hypomethylating agent (Cycle 1) may be started earlier, after 5 days of exposure to ENTO, if the Principal Investigator agrees with the treating physician that treatment should start sooner. Examples of such situations may include but are not limited to:

- White blood cell count is increasing and greater than 20,000/ μ L
- Leukemic related complications that in the opinion of the treating physician require the initiation of cytotoxic chemotherapy sooner

Hydroxyurea is allowed during the lead-in period per investigator discretion and after discussion with the medical monitor. Hydroxyurea should be discontinued prior to initiating hypomethylating agent.

A bone marrow aspirate for disease assessment will be performed at the end of the monotherapy lead-in period (ie, Cycle 0 Day 14 or after the minimum 5 days of ENTO) and prior to initiating therapy with hypomethylating agent.

Subjects with cytogenetic and molecular mutations at screening must have cytogenetic and molecular mutation testing repeated at subsequent bone marrow examinations (Cycle 0 Day 14, Cycle 1 Day 28, count recovery, End of Study).

Entospletinib Randomization lead-in (Cycle 0): ENTO 400 mg will be administered orally every 12 hours on Days 1-5 as a single agent during the lead-in.

Hydroxyurea is allowed during the lead-in period per investigator discretion and after discussion with the medical monitor. Hydroxyurea should be discontinued prior to initiating hypomethylating agent.

If circulating blasts have cleared at the end of monotherapy lead-in (Cycle 0 Day 5), then a bone marrow aspirate will be performed for disease assessment.

Subjects with cytogenetic and molecular mutations at screening must have cytogenetic and molecular mutation testing repeated at subsequent bone marrow examinations (Cycle 0 Day 5, Cycle 1 Day 28, count recovery, End of Study).

Entospletinib + Hypomethylating agent induction (Cycles 1-4): In subsequent induction cycles (Cycles 1-4), ENTO 400 mg will be administered orally every 12 hours on Days 1-28 in combination with the assigned hypomethylating agent dose and schedule. All subjects will receive at least 2 but no more than 4 cycles of induction chemotherapy.

Table 3-3. Hypomethylating Agent Dose and Schedule Table (Induction)

Agent	Dose	Days	Cycle Duration
decitabine	20mg/m ²	1-10	28 days
azacitidine	75mg/m ²	1-7	

A bone marrow aspirate and biopsy sample will be collected for disease assessment and biomarker research at the end of every 2 cycles (Cycle 2 Day 28 and Cycle 4 Day 28) or as clinically indicated. Subjects with cytogenetic and molecular mutations at screening must have cytogenetic and molecular mutation testing repeated at subsequent bone marrow examinations (Cycle 0 Day 14, Cycle 1 Day 28, count recovery, End of Study).

If the subject achieves < 5% blasts by morphology and flow cytometry or has evidence of clinical benefit after completing 2-4 induction cycles but is not eligible for SCT, the subject will have the option to receive maintenance therapy with ENTO in combination with decitabine or azacitidine. Subjects with persistent evidence of disease (ie, blasts ≥ 5%) after Cycle 2 may receive up to 2 more induction cycles until subject achieves < 5% blasts.

If < 5% blasts by morphology and flow cytometry is not achieved or the subject does not show evidence of clinical benefit after 4 induction cycles, the subject is considered a treatment failure and will have met study efficacy endpoint criteria, but will remain on study for required study-related follow-up procedures.

Entospletinib + Hypomethylating agent maintenance (at least 2 cycles): ENTO will be administered orally every 12 hours on Days 1-28 in combination with assigned hypomethylating agent dose and schedule.

Table 3-4. Hypomethylating Agent Dose and Schedule Table (Maintenance)

Agent	Dose	Days	Cycle Duration
decitabine	20mg/m ²	1-5	28 days
azacitidine	75mg/m ²	1-7	

A bone marrow aspirate sample will be collected at the end of every 4 cycles (eg, Cycle 4 Day 28, Cycle 8 Day 28) or as clinically indicated for disease assessment and biomarker research. Subjects who achieve CR/CRi that is stable for 2 consecutive bone marrow evaluations are not required to have further bone marrow aspirate samples collected, unless clinically indicated.

[figure not shown]
After completing at least 2 cycles, the subject may proceed to SCT. If not eligible for SCT, subjects will have the option to continue on maintenance therapy with ENTO in combination with the assigned hypomethylating agent. Subjects who are intolerant of the hypomethylating agent after completing 2 cycles may switch to ENTO monotherapy maintenance. Maintenance may continue as long as the subject is experiencing benefit and does not meet the criteria for study treatment discontinuation.

Entospletinib maintenance (maximum up to 12 cycles): ENTO 400 mg will be administered every 12 hours as a single agent on Days 1-28 of each 28-day cycle and will continue for up to 12 cycles as long as the subject is experiencing benefit and does not meet the criteria for study treatment discontinuation.

A bone marrow aspirate sample will be collected for disease assessment and biomarker research at the end of every 4 cycles (eg, Cycle 4 Day 28, Cycle 8 Day 28) or as clinically indicated. Subjects who achieve CR/CRi that is stable for 2 consecutive bone marrow evaluations are not required to have further bone marrow aspirate samples collected, unless clinically indicated.

If a subject discontinues study treatment (eg, as a result of an AE), every attempt should be made to keep the subject in the study to perform the required study-related follow-up and procedures. If this is not possible or acceptable to the subject or investigator, the subject may be withdrawn from the study.

Figure 3-3. Group B Phase 2 Randomization Dosing Schema

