ENTO will be administered orally every 12 hours as a monotherapy lead-in on Days 1-14 (Cycle 0), and will be administered orally every 12 hours on Days 1-28 in combination with decitabine on Days 1-10 of every 28-day cycle for at least 2 but no more than 4 cycles of induction chemotherapy. Subject will undergo a bone marrow aspiration and biopsy on Cycle 2 Day 28. Subjects who have a CR/CRi can proceed to SCT per investigator's discretion or to maintenance therapy with ENTO + decitabine. Subjects with persistent AML will receive 2 more cycles of induction chemotherapy and a bone marrow aspiration and biopsy will be performed at Cycle 4 Day 28. Subjects who have persistent leukemia at this time point will be considered a treatment failure and come off study. Subjects ineligible for SCT will have the option to receive maintenance therapy with ENTO + decitabine. Subjects who are intolerant of decitabine after completing 2 cycles will switch to ENTO monotherapy maintenance. Maintenance will continue as long as the subject experiences benefit and does not meet criteria for study treatment discontinuation. Extension of maintenance may occur on an individual basis if approved by the Principal Investigator.

Group B Phase 2 (Dose Expansion)

Note: At the time of this amendment, Group B Phase 2 safety run-in had completed enrollment. In Phase 2, the overall safety of ENTO in combination with a hypomethylating agent (decitabine or azacitidine)

will be evaluated. As part of the safety run-in, ENTO in combination with azacitidine will be administered to 6 evaluable subjects. Following completion of the safety run-in (DLT window, Section 3.2), the azacitidine arm will be evaluated to determine if enrollment of the expansion cohort may proceed with azacitidine. If 2 or more subjects experience DLTs, all ongoing subjects in the safety run-in will be discontinued, the azacitidine arm will be dropped from the study, and subjects in the expansion phase will only receive ENTO in combination with decitabine.

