ENTO lead-in will be administered every 12 hours on Days 1-14 as a single agent (Cycle 0) for subjects enrolled to Group B Phase 1b and Group B Phase 2 safety run-in. However, chemotherapy with the assigned hypomethylating agent (Cycle 1) may be started earlier, after 5 days of exposure to ENTO, if the Principal Investigator agrees with the treating physician that treatment should start sooner.

For subjects enrolled to Group B Phase 2 randomization, ENTO lead-in will be administered every 12 hours on Days 1-5 as a single agent (Cycle 0).

In subsequent induction cycles (Cycles 1-4), ENTO will be administered every 12 hours on Days 1-28 in combination with assigned hypomethylating agent dose and schedule. Only azacitidine will be given during the Phase 2 safety run-in. Subjects will receive at least 2 cycles

of induction therapy but no more than 4 cycles. If the subject achieves < 5% blasts by morphology and flow cytometry or has evidence of clinical benefit after completing 2-4 induction cycles but is not eligible for SCT, the subject will have the option to receive maintenance therapy with ENTO in combination with decitabine or azacitidine. Subjects with persistent evidence of disease (ie, blasts \geq 5%) after Cycle 2 may receive up to 2 more induction cycles until subject achieves < 5% blasts. If < 5% blasts by morphology and flow cytometry is not achieved or the subject does not show evidence of clinical benefit after 4 induction cycles, the subject is considered a treatment failure and will be discontinued from the study.

During ENTO + hypomethylating agent maintenance therapy, ENTO will be administered every 12 hours on Days 1-28 in combination with assigned hypomethylating agent dose and schedule. ENTO will be administered every 12 hours on Days 1-28 in combination with decitabine on Days 1-5 or in combination with azacitidine on Days 1-7 of every 28-day cycle for at least 2 cycles. Subjects who are intolerant of the hypomethylating agent after completing 2 cycles may switch to ENTO monotherapy maintenance. Maintenance may continue as long as the subject is experiencing benefit and does not meet the criteria for study treatment discontinuation.

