During ENTO maintenance therapy, ENTO will be administered as monotherapy every 12 hours on Days 1-28. Treatment may continue until the subject meets the criteria for study treatment discontinuation or up to 12 cycles. Extension of maintenance may occur on an individual basis if approved by the Principal Investigator.

If a subject discontinues study treatment (eg, as a result of an AE), every attempt should be made to keep the subject in the study to perform the required study-related follow-up and procedures. If this is not possible or acceptable to the subject or investigator, the subject may be withdrawn from the study.

For subjects enrolled to Group C Phase 1b (Dose Escalation):

ENTO monotherapy will be administered every 12 hours on Days 1-28 of every 28-day cycle until the subject meets the criteria for study treatment discontinuation (see Section 6.4.1). Subjects who experience a DLT may continue on protocol at a de-escalated dose.

If a subject discontinues study treatment (eg, as a result of an AE), every attempt should be made to keep the subject in the study to perform the required study-related follow-up and procedures. If this is not possible or acceptable to the subject or investigator, the subject may be withdrawn from the study.

For subjects enrolled to Group C Phase 2 (Dose Expansion):

ENTO monotherapy will be administered every 12 hours on Days 1-28 of every 28-day cycle and may continue as long as the subject is experiencing benefit and does not meet criteria for study treatment discontinuation.

If a subject discontinues study treatment (eg, as a result of an AE), every attempt should be made to keep the subject in the study to perform the required study-related follow-up and procedures. If this is not possible or acceptable to the subject or investigator, the subject may be withdrawn from the study.

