6.5. Long Term Follow-up

Long term follow-up for survival will be conducted every 6 months (\pm 4 weeks) after the End of Study Treatment visit for up to 3 years (since the start of study therapy). Information to be gathered includes leukemia treatments, other malignancies, and survival. This follow-up can be done during a routine clinic visit, other contact with the subject, or via telephone. Gilead reserves the right to discontinue or shorten the duration of participation in the long term follow-up period at any time. See section [9.3.4](#) for details regarding study discontinuation.

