
No postbaseline assessment, no death
	
Censored
	
Date of first dose

No treatment failure/relapse/death
	
Censored
	
Date of last response assessment (and prior to other anti-cancer therapy if any) or first dosing date, whichever is later

Other anti-cancer therapy started prior to treatment failure/relapse/death	Censored	Date of last response assessment prior to other anti-cancer therapy or first dosing date, whichever is later
Days from last response assessment prior to treatment failure/relapse/death or first dosing date, whichever is later, to treatment failure/relapse/death was not within the window defined above	Censored	Date of last response assessment prior to treatment failure/relapse/death or first dosing date, whichever is later

Censoring Rules for OS:

- For a subject who is not known to have died by the end of study follow-up, OS is censored on the date the subject was last known to be alive.

For EFS or OS in months, the calculation is based on the following formula:

$$(\text{date of event/censoring} - \text{date of first dose} + 1) / 30.4375.$$

EFS and OS will be analyzed using Kaplan-Meier (KM) methods. The KM estimate of the survival function will be computed and the results will be presented using KM curves. The median will be provided along with the corresponding 95% CI. Additionally, the 25% and 75% percentiles for these endpoints will also be provided.

Follow up time for OS will be summarized as continuous variable with descriptive statistics.

- For a subject who is not known to have died by the end of study follow-up, duration of OS follow up in months = $(\text{date of last known to be alive} - \text{date of first dose} + 1) / 30.4375$
- For the remaining subjects, duration of OS follow up in months = $(\text{date of follow-up cutoff} - \text{date of first dose} + 1) / 30.4375$

Data listing for EFS and OS will be presented.

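### Group B treatment failures are taken off study in one protocol section and kept on study in others, which leaves their OS follow-up open to early, selective censoring; the maintenance and failure rules also overlap

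*Protocol*

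**What the plan says.** Protocol 3.1.4 (Group B Phase 2) offers maintenance with ENTO plus the hypomethylating agent to a subject who reaches <5% blasts "or has evidence of clinical benefit after completing 2-4 induction cycles but is not eligible for SCT". It then says that if <5% blasts "is not achieved or the subject does not show evidence of clinical benefit after 4 induction cycles, the subject is considered a treatment failure". Such a subject has met the efficacy endpoint criteria "but will remain on study for required study-related follow-up procedures". Protocol 3.1.3 (Phase 1b) and 6.3.2 (Group B procedures) have the same either/or structure and also keep failures on study.

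Protocol 3.4, under Group B Phase 1b/2, repeats the two rules but ends differently: "the subject is considered a treatment failure and will be discontinued from the study". Later in the same Group B text it says of anyone who stops study treatment that "every attempt should be made to keep the subject in the study to perform the required study-related follow-up and procedures".

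The synopsis for Group B Phase 1b, repeated in SAP 1.2, uses a third form with no clinical-benefit term: "Subjects who have persistent leukemia at this time point will be considered a treatment failure and come off study".

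OS is a secondary endpoint. For a subject not known to have died, SAP 6.2.2 says that "OS is censored on the date the subject was last known to be alive".

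**The concern.** The main issue is survival follow-up. A site that takes 3.4 at its word stops following a Group B subject at the moment induction is judged to have failed. Responders stay under observation and non-responders leave the risk set soon after Cycle 4. Kaplan-Meier estimation assumes that censored subjects have the same future hazard as those still followed. If failures have the worse prognosis, which is an assumption here, that fails and the OS curve is too high.

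The second issue is the treatment instruction. A subject with persistent blasts who is benefiting can be offered maintenance under one sentence and called a failure under another. The failure sentences do not themselves order treatment to stop. The implied stop comes from the synopsis entry on duration of treatment, which lets subjects receive ENTO until treatment failure.

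**Working it through.** **What happens to a Group B failure.** Setting the texts side by side:

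| Place | Covers | Instruction |
|---|---|---|
| Protocol 3.1.3 | Group B Phase 1b | Failure stays on study |
| Protocol 3.1.4 | Group B Phase 2 | Failure stays on study |
| Protocol 6.3.2 | Group B procedures | Failure stays on study |
| Protocol 3.4, Group B | Phase 1b and Phase 2 | Failure is discontinued from the study |
| Protocol 3.4, Group B, closing paragraph | Anyone stopping treatment | Keep on study if at all possible |
| Synopsis and SAP 1.2 | Group B Phase 1b only | Failure comes off study |
| Protocol 3.4, Group A Phase 2 | Group A failures | Failure stays on study |
| Protocol 6.5 and both Group B schedules in Appendix 2 | All subjects | Six-monthly survival contacts to 3 years, no exception for failures |
| Protocol 6.4.1 | Subject asks to stop treatment | Still followed for survival to 3 years |

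For Phase 2 the contrary text is the one phrase in 3.4. For Phase 1b it is that phrase plus the synopsis and SAP 1.2. Sections 3.1.3, 3.1.4 and 6.3.2 speak of required follow-up procedures without naming survival; that survival is included comes from 6.5, 6.4.1 and the schedules.

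**Bounds on follow-up lost, for one subject failing at Cycle 4 Day 28.**
- Lower bound: 0 months, if the site follows 3.1.4, 6.3.2 and 6.5.
- Study day at failure: 5 + 4×28 = 117 with the 5-day lead-in; 14 + 4×28 = 126 with the 14-day lead-in.
- Upper bound: (3×365.25 − 117)/30.4375 = 32.2 months, or (3×365.25 − 126)/30.4375 = 31.9 months, of 36.
- Contacts missed at the upper bound: starting from month 3.84, contacts fall near months 9.8, 15.8, 21.8, 27.8 and 33.8, so five. The 14-day lead-in also gives five.

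The upper bound needs a literal reading of 3.4, a subject who survives three years, and no shortening of follow-up by the sponsor. The documents do not give the number of subjects affected, so no OS bias can be computed.

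**Overlap of the two rules.** For a subject not eligible for SCT at the end of induction:

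| <5% blasts | Clinical benefit | Maintenance (either present) | Failure as written (either absent) | Failure if defined as neither |
|---|---|---|---|---|
| Yes | Yes | Yes | No | No |
| Yes | No | Yes | **Yes** | No |
| No | Yes | Yes | **Yes** | No |
| No | No | No | Yes | Yes |

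Two of four combinations meet both rules as written. The practical one is the third row. Defining failure as neither leaves no overlap and no combination without a rule. Footnote e in both Group B schedules names only <5% blasts for going on to maintenance, which points the other way for that third row.

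**Reach into the analysis.** Appendix 5 and SAP 6.1.2 and 6.2.2 define treatment failure by response assessments, with no clinical-benefit term. The site's label therefore does not itself set CR, CR/CRi, overall response or EFS status. SAP 6.2.2 does use all assessments before SCT or other anticancer therapy and dates failure at the last adequate one; best overall response in SAP 6.1.2 likewise spans all such time points. Whether treatment stops or continues can therefore change which later assessments exist for those two analyses.

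**The case against.** The strongest reply is that the protocol already answers the follow-up question. Sections 3.1.3, 3.1.4, 6.3.2 and 6.5 and both schedules point to continued follow-up. The phrase in 3.4 sits in a section about treatment duration, and the protocol uses the word study loosely: Section 6.4 is titled for discontinuation from study but deals with stopping treatment. This stands as a reason to expect a small effect. It does not remove the conflict, because 3.4 itself says that Group A failures remain on study, so the different Group B wording can be read as deliberate.

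On the overlap, the failure sentence can be read as the plain negation of the maintenance sentence, meaning neither condition is met. The failure sentences contain no order to stop drug, and treatment failure is not among the discontinuation criteria in 6.4.1. That is fair, and it is why the overlap is the secondary point. The literal text still negates each condition separately, the synopsis and SAP 1.2 use persistent leukemia alone, and footnote e uses blasts alone.

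Finally, recruitment is closed and SAP Section 1 says the study will end early, so rewording has limited prospective value. That stands, and it shifts the weight to what the study report should check.

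**Conclusion.** The conflict over follow-up is real and worth correcting. Its effect on OS is somewhere between nothing and an unquantified upward bias, probably small, because most of the text already requires follow-up, 6.5 lets the sponsor shorten it, and the study is ending early. The direction rests on two assumptions: that some sites followed 3.4 literally, and that non-responders die sooner.

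The documents do not support three stronger readings that a reader might infer.
- That each failure loses about 32 months of follow-up. This is a ceiling for someone alive at three years, which sits awkwardly with the assumption of early death that drives the bias.
- That the response rates or EFS are misclassified by the site's failure label. They are derived from response assessments. The only route is indirect, through which later assessments exist for EFS and best overall response.
- That half of Group B subjects face contradictory rules. Two of four logical combinations overlap, but that is not a proportion of subjects, and only the case of ≥5% blasts with clinical benefit is practical.

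**What to change.** 1. In Protocol 3.4 (Group B), the synopsis (Group B Phase 1b) and SAP 1.2, replace the off-study wording with: *stops study treatment and remains on study for follow-up including survival*. This brings Group B into line with Group A in 3.4.
2. In Protocol 3.1.3, 3.1.4, 3.4 and 6.3.2, define failure as having neither <5% blasts nor evidence of clinical benefit at the end of induction. Use the same criterion in the synopsis and SAP 1.2 in place of persistent leukemia alone; otherwise the Phase 1b overlap survives the edit. Align footnote e in both Group B schedules with the maintenance rule.
3. In the study report, identify Group B failures whose survival follow-up ended at treatment failure, using the response, study-discontinuation and OS listings already planned in SAP 6.1.2, 4.1 and 6.2.2. State how many there were and when their OS was censored.

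The cost is wording in four protocol sections, the synopsis, SAP 1.2 and two footnotes, plus one cross-check of planned listings. No endpoint is redefined and no new data are needed.
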